17.2. Recommendations per CHEST 2012 Guidelines¹¹

Table 17.2 shows the initial treatment and prophylactic doses of LMWH that are used in pediatric subjects based on age.

Drug	Age	Initial Treatment Dose	Initial Prophylactic Dose
Age-Dependent Dose	<2 months	1.5 mg/kg/dose q12h	0.75 mg/kg/dose q12h
of Enoxaparin	>2 months	1.0 mg/kg/dose q12h	0.5 mg/kg/dose q 12h
Enoxaparin has 110 anti-	-Factor Xa uni	ts/mg	
Recommended target and	ti-FXa range fo	or LMWH is 0.5 to 1.0 IU/mL.	
Note: The anti-FXa assa inhibition of Factor Xa is	y detects hepain n the assay rea	rin in subject's plasma based on gent.	

 Table 17.2:
 Doses of LMWH (enoxaparin) Used in Pediatric Subjects

Table 17.3 shows the protocol for anticoagulation therapy to maintain an INR between 2 and 3 for pediatric subjects on warfarin therapy.

Table 17.3:Protocol for Anticoagulation Therapy to Maintain an INR Between 2 and 3
for Pediatric Subjects (Warfarin Treatment)

1	Day 1: if the baseline INR is 1.0 to 1.3: Dose 0.2	mg/kg orally
	·	
2	Loading 0.2 mg/kg Days 2-4: if the INR is:	
	INR	Action
	1.1 – 1.3	Repeat initial loading dose
	1.4 - 1.9	50% of initial loading dose
	2.0 - 3.0	50% of initial loading dose
	3.1 – 3.5	25% of initial loading dose
	>3.5	Hold until INR <3.5; then restart at 50% decreased dose
3	Maintenance oral anticoagulation dose guidelines	:
	INR	Action
	1.1 -1.4	Increase by 20% of dose
	1.5 – 1.9	Increase by 10% of dose
	2.0 - 3.0	No change
	3.1-3.5	Decrease by 10% of dose
	>3.5	Hold until INR <3.5; then restart at 20% decreased dose

Abbreviations: INR = international normalized ratio

17.3. Effective Methods of Birth Control

Women of childbearing age are defined as those females that have reached menarche and until becoming postmenopausal unless permanently sterile (defined as no menses for 12 months without an alternative medical cause) and are eligible for the study based on the inclusion and exclusion criteria.

Female subjects of childbearing potential must test negative for pregnancy at Randomization (with a highly sensitive test) and must consent to avoid becoming pregnant by using an approved contraception method throughout the study.

The following use of reliable method(s) of contraception, and/or abstinence, for the duration of therapeutic product exposure is recommended:

Highly effective methods of contraception, when used consistently and correctly, result in low failure rates. These may include:

• Combined (estrogen and progesterone-containing) hormonal contraception associated with inhibition of ovulation

Oral

Intravaginal

Transdermal

• Progresterone-only hormonal contraception associated with inhibition of ovulation

Oral

Injectable

Implantable

- Intrauterine device (IUD)
- Intrauterine hormonal-releasing system
- Bilateral tubal occlusion
- Vasectomized partner
- Sexual abstinence

Effective methods may include:

• Barrier methods of contraception (eg, male condom, female condom, cervical cap, diaphragm, contraceptive sponge).

Note: When used consistently and correctly, "double barrier" methods of contraception (eg, male condom with diaphragm, male condom with cervical cap) can be used as an effective alternative to the highly effective contraception methods described above.

Only in individual cases where the stable use of highly effective methods is medically contraindicated (investigator's written documentation required), double barrier methods may be acceptable.

Oral contraception is not contraindicated with edoxaban but maybe not recommended in patients with high risk of thromboembolic events. The use of oral contraception is per Investigator's discretion.

17.4. Contraindications for Standard of Care Therapy

Contraindications to warfarin (COUMADIN):

- Hypersensitivity to the active substance or to any of the excipients
- Hemorrhagic stroke
- Clinically significant bleeding
- Use within 72 hours of major surgery with risk of severe bleeding
- Use within 48 hours postpartum
- Pregnancy
- Drugs where interactions may lead to a significantly increased risk of bleeding

Contraindications to enoxaparin (LOVENOX):

- Hypersensitivity to either enoxaparin sodium, heparin or its derivatives including other LMWH
- Acute bacterial endocarditis
- Active major bleeding
- Conditions with a high risk of uncontrolled hemorrhage, including recent hemorrhagic stroke or thrombocytopenia in subjects with a positive in-vitro aggregation test in the presence of enoxaparin; active gastric or duodenal ulceration
- Subjects receiving heparin for treatment rather than prophylaxis

Note: Loco-regional anesthesia in elective surgical procedures is contraindicated.

Contraindications to UFH:

- History of heparin-induced thrombocytopenia (with or without thrombosis)
- Uncontrolled, active bleeding (except disseminated intravascular coagulation)
- Acute bacterial endocarditis
- When suitable, blood-coagulation tests (eg, the whole-blood clotting time, partial thromboplastin time, etc) cannot be performed at appropriate intervals
- Hypersensitivity to heparin
- Advanced renal or hepatic dysfunction
- Severe hypertension
- Major surgery involving the brain, spinal cord and eye.

17.5. Prohibited Concomitant Medications at Any Time during the Treatment Period with Edoxaban or SOC

The list here (in the protocol) is static and reflects the list at the time of the current version of the protocol. If there are changes to this list during the study, the changes will not be considered a protocol amendment and the list in this appendix will not be updated unless the protocol is being amended for other reasons as well.

Subjects on these drugs at the time of planned randomization will be excluded from the study. After randomization, use of these drugs will require a study drug permanent discontinuation unless advised otherwise in the Sections below. The Investigator is encouraged to contact the Medical Monitor for further guidance.

Sites will receive a contact card where the following numbers (24-hour Urgent Medical Contact) are provided:

17.5.1. Antiplatelet Drugs

Use of any antiplatelet medication as single or dual agent antiplatelet therapy is prohibited while on study drug except for low dose aspirin defined as 1 to 5 mg/kg/day with maximum of 100 mg/day. If there is a clinical indication for single or dual agent antiplatelet therapy, the subject will need to be discontinued from the study treatment.

Examples of non-aspirin oral antiplatelet agents include the following:

- Thienopyridines: clopidogrel (Plavix®), ticlopidine (Ticlid®), prasugrel (Effient®)
- Dipyridamole: Persantine®, Aggrenox®
- Cilostazol (Pletal®)
- Pentoxifylline (Trental®)
- Sulfinpyrazone (Anturane®)
- Ticagrelor (Brillanta®)

IV antiplatelet agents include the following:

- Glycoprotein IIb/IIIa inhibitors: Abciximab (ReoProTM), Eptifibatide (Integrilin®),
- Tirofiban (Aggrastat®)
- P2Y12 Inhibitor: Cangrelor
- Dextran

17.5.2. Oral Anticoagulants Other than Study Drug

Oral anticoagulants including Factor IIa inhibitors (eg, dabigatran), and FXa inhibitors (eg, rivaroxaban, apixaban) are prohibited in both treatment arms. The only allowed oral anticoagulants are the study drugs.

17.5.3. Parenteral Anticoagulants

Parenteral anticoagulants are prohibited in the edoxaban-treatment arm. Direct thrombin inhibitors are prohibited in both the edoxaban arm and in the SOC arm.

Examples of prohibited parenteral anticoagulant medications include the following:

- LMWH: enoxaparin (Lovenox®, Clexane®), dalteparin (Fragmin®), tinzaparin (Innohep®, Logiparin®), reviparin (Clivarin®), nadroparin (Fraxiparine®), ardeparin (Normiflo®), certoparin (Sandoparin®), parnaparin (Fluxum®)
- UFH: Calciparine®
- Direct thrombin inhibitors: bivalirudin (Angiomax®), argatroban, (Acova®), desirudin (Iprivask®), lepirudin (Refludan®)
- FXa inhibitors: fondaparinux (Arixtra®)

17.5.4. Intravenous Fibrinolytics

Intravenous fibrinolytics are prohibited in both treatment arms. Examples of fibrinolytics include the following:

- Tissue plasminogen activator (tPA, alteplase, Activase®),
- TNK (tenecteplase, TNKase®),
- rPA (reteplase, Retavase®),
- Streptokinase (Streptase®),
- Anistreplase (Eminase®).

If a subject requires treatment with a fibrinolytic agent, then study drug must be discontinued.

17.5.5. Non-Steroidal Anti-Inflammatory Drugs (excluding aspirin)

While on study drug, NSAIDs cannot be taken for ≥ 4 days per week. Less frequent use of NSAIDs is permitted while on study drug. However, the Investigator should weigh the benefit/risk of NSAID use in combination with an oral anticoagulant for the individual subject. Table 17.4 lists examples of NSAIDs.

Protocol DU176b-C-U313 Version 4.0, 03 JUN 2019

Aceclofenac	Acemetacin	Alclofenac
Amtolmetin	Azapropazone	Benoxaprofen
Bromfenac	Bufexamac	Carprofen
Clonixin	Dexibuprofen	Dexketoprofen
Diclofenac	Diclofenac/Hyaluronic Acid	Diflunisal
Dipyrone	Droxicam	Etodolac
Etofenamate	Felbinac	Fenbufen
Fenoprofen	Fentiazac	Floctafenine
Flufenamic Acid	Flurbiprofen or Fluribuprofen	Hydrocodone/Ibuprofen
Ibuprofen	Indomethacin	Indoprofen
Isoxicam	Ketoprofen	Ketorolac
Lansoprazole/Naproxen	Lornoxicam	Loxoprofen
Meclofenamate	Mefenamic Acid	Meloxicam
Morniflumate	Nabumetone	Naproxen
Niflumic Acid	Nimesulide	Oxaprozin
Oxycodone/Ibuprofen	Phenylbutazone	Piketoprofen
Pirazolac	Piroxicam	Pirprofen
Prophenazone	Proquazone	Sulindac
Suprofen	Tenidap	Tenoxicam
Tiaprofenic Acid	Tolmetin	Zomepirac

Table 17.4: Thorough List of NSAIDs

17.5.6. P-gp Inducers (Prohibited Medication)

Rifampin is a P-gp inducer that has been shown to lower the edoxaban exposure Therefore, concomitant use of rifampin is contraindicated during the treatment period. Other P-gp induces may lead to a lower exposure of edoxaban than predicted for clinical efficacy. The example medications listed below (but not limited to) have not been tested with edoxaban but are also P-gp inducers. These should be avoided during the study as their use may lead to a lower exposure of edoxaban than predicted for clinical efficacy. (http://www.straighthealthcare.com/p-glycoprotein.html#inducers).

- Rifampin
- Carbamazepine (Tegretol®)

17.6. Concomitant Medications that Require Edoxaban Dose Adjustment

17.6.1. P-gp Inhibitors List

Use of P-gp inhibitors during the treatment with edoxaban will require dose reduction either at randomization or during the course of the study. These drugs can potentially raise the exposure level of edoxaban. The only exemption from this rule is the use of amiodarone which will not require dose reduction.

Table 17.5 shows examples (not limited to) of the most commonly used P-gp inhibitors:

Drug Class	Drug Name
Antiarrhythmics	Amiodarone, quinidine, verapamil, dronedarone, carvedilol, ranolazine.
Antibiotics	Clarithromycin.
Anti-fungal	Itraconazole
Others	Lapatinib, lopinavir, ritonavir, propafen

Table 17.5:P-gp Inhibitors List

17.7. Transition From Edoxaban to Other Anticoagulants

Subjects who require anticoagulation at the end of study participation will be transitioned to standard-of-care treatment as directed by the Investigator or treating physician.

At the end of edoxaban treatment, the subject will receive the last dose of edoxaban and all remaining edoxaban tablets/bottles will be collected from the subject by site staff.

Subjects transitioning from edoxaban to any VKA will have their INR recorded at last study visit. Bridging with heparin may occur during VKA titration until the INR is at a therapeutic level of 2 to 3.

INR will need to be measured as frequently as necessary until the INR target of ≥ 2 . Once the INR is ≥ 2.0 the heparin will be stopped and the subject will continue on the VKA alone.

When transitioning from edoxaban to another direct oral anticoagulant (e.g. rivaroxaban, apixaban, dabigatran):

• The first dose of the direct oral anticoagulant of choice will be given 24 hours post the last dose of edoxaban and will then be continued as per the novel anticoagulant's label.

For subjects who do not complete the Main Treatment Period, they will be followed with monthly visits until the end of Month 3 and have a 30-day Follow-Up Visit according to the Schedule of Events (Appendix 17.1).

For subjects who complete the Main Treatment Period but do not continue into the Extension Treatment Period, the subjects will receive a Discontinuation Visit and a Follow-Up Visit, 30 days after last dose of study drug.

For subjects who continue into the Extension Period, the Follow-Up Visit will occur 30 days after the Discontinuation Visit (Month 12, Visit 8).

17.8. Management of Serious/Life-Threatening Bleeding

The following steps are currently recommended for subjects with ongoing major bleeding (see Section 9.1):

- Withhold study drug and all antiplatelets/anticoagulants
- Institute SOC for major bleeding (large bore IV or central venous line, type and crossmatch blood, admit to the intensive care unit, provide hemodynamic and respiratory support)
- Administer packed red blood cells (or whole blood) as needed
- Administer antidotes if applicable

For UFH/LMWH:

The antidote for UFH/LMWH is protamine sulfate. The dose of protamine sulfate given is dependent upon the dose of UFH/LMWH administered and the time of administration.

Suggestions from the Sponsor:

- If protamine is given within 8 hours of the UFH/LMWH then a maximum neutralizing dose is 1 mg protamine/100 units (or 1 mg) of UFH/LMWH given in the last dose.
- If more than 8 hours have passed since the dose of UFH/LMWH was given, administer 0.5 mg protamine per 1 mg (100 units) of UFH/LMWH given.

Protamine is administered by slow IV infusion (over 10 minutes) to avoid a hypotensive reaction. Protamine is a medication that requires a high level of caution when being prescribed and administered. Outside cardiac surgery and intensive care unit (ICU), consultant or fellow approval is required for the use of protamine- do not allow this to lead to delayed administration in the case of bleeding. Contact the appropriate senior person immediately.

For Warfarin:

If a subject has significant but not life-threatening bleeding: Administer Vitamin K 0.5 mg to 2 mg SC (NOT intramuscularly) plus fresh frozen plasma (20 mL/kg IV) to a maximum of 4 units.

If a subject has major bleeding (any INR) or requires emergency surgery doses because their INR >8:

- Stop Warfarin
- Vitamin K (30 μ g/kg) IV, consider higher doses if INR >8
- Prothrombin complex concentrate (PCC) replacement therapy (To note: fresh frozen plasma gives inferior correction and is not recommended):

Beriplex® [4-factor Prothrombin Complex Concentrate approved in several European countries] (and Kcentra® approved in the United States) (Discuss with on call hematologist). Beriplex dosage is calculated based on the current INR and subject's weight (see Table 17.6)

Repeat the INR following PCC

Further doses of Beriplex or Vitamin K may be required

INR	Approximate Dose
2.0-3.9	1 mL/kg = 25 IU/kg
4.0-6.0	1.4 mL/kg = 35 IU/kg
>6.0	2 mL/kg = 50 IU/kg

Table 17.6: Dose Adjustments for INR Elevation

For Edoxaban:

Although not evaluated in clinical trials, PCC, activated PCC, or recombinant Factor VIIa could be considered for the reversal of the anticoagulant effect of edoxaban. In healthy volunteers, a 3-factor PCC restored thrombin generation (area under the curve for thrombin generation curve) but did not normalize PT. Thus, a 3-factor PCC may be of some value in reversing anticoagulant effects of edoxaban (Study A-U150).

A specific reversal agent for edoxaban is not available. Although not evaluated in subjects, PCC (Beriplex® or Kcentra®), activated PCC, or recombinant Factor VIIa could be considered for the reversal of the anticoagulant effect of edoxaban.

The following are not expected to reverse the anticoagulant effects of edoxaban:

- Protamine sulfate,
- Vitamin K,
- Tranexamic acid.

Hemodialysis does not significantly contribute to edoxaban clearance.

In the event of a Medical Emergency, the Investigator at the clinical site will institute any medical procedures deemed appropriate. A 24-hour Urgent Medical Contact will be provided to contact the Medical Monitor for further guidance.

Sites will receive a contact card where the following numbers (24-hour Urgent Medical Contact) are provided:

PPD (primary number)
PPD (alternative number)

The medical call center will contact Medical Monitor for the assigned region.

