9. SAFETY EVALUATION AND REPORTING

9.1. Assessment of Safety Endpoint(s)

The safety endpoints related to safety objectives are bleeding events, including major, clinical relevant non-major and minor bleeding. All potential bleeding events will be adjudicated by an independent CEC. Study endpoints and safety data will be periodically reviewed by an IDMC to ensure the safety of study participants.

Bleeding definitions are based on the ISTH modified recommendations¹,

• Major bleeding is defined as a composite (ie, any) of the following:

Fatal bleeding; and/or

Symptomatic bleeding in a critical area or organ, such as intracranial, intra-spinal, intraocular, retroperitoneal, intra-articular, pulmonary, or pericardial, or intramuscular with compartment syndrome; and/or

Bleeding causing a decrease in hemoglobin level of 2 g/dL (1.24 mmol/L) or more, or leading to transfusion of the equivalent of two or more units of whole blood or red cells.

• A CRNM bleed is an acute or sub-acute clinically overt bleed that does not meet the criteria for a major bleed but prompts a clinical response, in that it leads to at least one of the following:

A hospital admission for bleeding, or

A physician guided medical or surgical treatment for bleeding, or

A change in antithrombotic therapy (including interruption or discontinuation of study drug).

• Minor bleeding is defined as any other overt bleeding event that does not meet criteria for either major bleeding or clinically relevant, non-major bleeding.

Minimal criteria defining a significant bleeding per ISTH¹⁰ are as follows:

For each specific bleeding symptom, the ISTH/Scientific and Standardization Committee (SSC) joint working group proposed minimal criteria in order to classify a symptom as significant:

- 1. Epistaxis:
 - Any nosebleed, especially occurring after puberty that causes subject concern (eg, interference or distress with daily or social activities) is considered significant.
 - In general, epistaxis should not be considered significant when it lasts less than 10 minutes, has a frequency of <5 episodes/year, has a seasonal occurrence, or is associated with infections of the upper respiratory tract or other identifiable cause (e.g., dusty dry air).
- 2. Cutaneous bleeding:
 - Bruises are considered significant when 5 or more (>1 cm) in exposed areas;

- Petechiae are considered significant when adequately described by the subject or relatives;

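### In Appendix 17.8, a major bleed on warfarin that does not threaten life meets both reversal branches, and the two contradict each other on fresh frozen plasma, PCC and vitamin K route

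*Combined protocol and SAP*

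**What the plan says.** Appendix 17.8 opens with its scope: "The following steps are currently recommended for subjects with ongoing major bleeding (see Section 9.1"). Everything for warfarin sits under that sentence, in two branches.

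- First branch: "If a subject has significant but not life-threatening bleeding: Administer Vitamin K 0.5 mg to 2 mg SC (NOT intramuscularly) plus fresh frozen plasma", the plasma at 20 mL/kg up to 4 units.
- Second branch: "If a subject has major bleeding (any INR) or requires emergency surgery doses because their INR >8". Here warfarin is stopped, vitamin K is given intravenously at 30 micrograms/kg, and PCC is given by INR and weight from Table 17.6. A note in the PCC entry says that "fresh frozen plasma gives inferior correction and is not recommended".

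Section 9.1 lists the criteria for a major bleed, any one of which is enough. One is "Bleeding causing a decrease in hemoglobin level of 2 g/dL (1.24 mmol/L) or more"; another is transfusion of at least two units of whole blood or red cells. Neither requires a threat to life.

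For heparins, Appendix 17.8 suggests that within 8 hours "a maximum neutralizing dose is 1 mg protamine/100 units (or 1 mg) of UFH/LMWH given in the last dose", and half that after 8 hours. Appendix 17.2 says "Enoxaparin has 110 anti"-Factor Xa units per mg.

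**The concern.** A site treating a warfarin subject should be able to tell which branch applies. The first trigger sorts bleeds by threat to life, the second by the Section 9.1 major category. These are different axes, so a bleed can satisfy both. Where it does, one branch gives plasma and the other advises against it.

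Appendix 17.8 is the only reversal guidance in the protocol, and the trial's primary endpoint is major and clinically relevant non-major (CRNM) bleeding in children. At stake is whether sites managing the same kind of comparator-arm bleed receive one instruction or two.

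**Working it through.** **Do the triggers overlap?** Take a warfarin subject with an ongoing bleed, a hemoglobin fall of 2 g/dL and no threat to life.

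1. Section 9.1: the hemoglobin criterion is met, so the bleed is major.
2. Appendix 17.8 scope: ongoing major bleeding, so the appendix applies.
3. Second branch: major bleeding at any INR, so it applies.
4. First branch: the bleed is not life-threatening, and a bleed that meets a major criterion can hardly be called less than significant, so it applies too.

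**What does each branch say for that subject?**

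| Item | First branch | Second branch |
|---|---|---|
| Fresh frozen plasma | Given, 20 mL/kg, up to 4 units | Not recommended |
| PCC | Not mentioned | Given, per Table 17.6 |
| Vitamin K route | Subcutaneous | Intravenous |
| Vitamin K amount | 0.5 to 2 mg, fixed | 30 micrograms/kg |

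The plasma row is a direct contradiction. The PCC and route rows give different instructions for the same subject.

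**Vitamin K amounts.** The per-kg amount equals the fixed limits at:

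- 0.5 mg / 0.030 mg/kg = 16.7 kg
- 2 mg / 0.030 mg/kg = 66.7 kg

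At 10 kg it is 10 × 0.030 = 0.30 mg, below the first branch's minimum. At 45 kg it is 1.35 mg, inside the range. At 80 kg it is 2.4 mg, above the maximum. Children under 16.7 kg are eligible, since enrollment starts at 1 year and may later extend to 38 weeks gestational age.

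**INR coverage.** The second branch applies at any INR, but the lowest row of Table 17.6 is INR 2.0 to 3.9. The protocol foresees lower values on warfarin: its maintenance guidance has rows for INR 1.1 to 1.4 and 1.5 to 1.9. The three rows of Table 17.6 agree with one another: 25/1, 35/1.4 and 50/2 are all 25 IU/mL.

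**Protamine.** Within Appendix 17.8 both lines use 1 mg = 100 units; 1 mg and 0.5 mg of protamine differ only by time since the last dose. The mismatch is with Appendix 17.2. For 60 mg of enoxaparin:

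- By mass: 60 mg protamine within 8 hours, 30 mg after.
- By units: 60 × 110 = 6600 units; 6600/100 = 66 mg within 8 hours, 33 mg after.
- Ratio: 66/60 = 1.10, a 10% difference.

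**The case against.** The strongest reply is that the branches are tiers: the first for bleeds below major, the second for every major bleed, with the remark against plasma confined to the second. That may be what was meant, but it is not written. It would also put the first branch outside the appendix's own scope sentence. Nor is significant bleeding a tier below major in Section 9.1. It is a separate list of symptom criteria that includes subdural and intracerebral hemorrhage, while symptomatic intracranial bleeding is major.

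A second reply is that the steps are only recommended, that the investigator may act as judged appropriate with a 24-hour medical contact, that the PCC entry calls for discussion with a hematologist, and that standard of care varies by site by design. This stands as mitigation and limits the weight of the point. It does not tell a site which branch applies.

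A reader might infer three stronger things that the documents do not support:

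- **That the vitamin K amounts are themselves a contradiction.** The routes differ, the second branch adds PCC, and it allows for higher and further doses. Nothing in the protocol says that a worse bleed must receive more milligrams.
- **That the protamine lines conflict with each other.** They agree. The 10% difference is between Appendices 17.2 and 17.8, concerns enoxaparin only, and appears only if a milligram dose is first converted to units. The protocol states enoxaparin doses in mg.
- **That the primary comparison is distorted.** The major criterion counts whole blood or red cells, not plasma or PCC, and either regimen is physician-guided treatment under the CRNM definition. The choice of branch does not by itself change how a bleed is classified.

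**Conclusion.** The point holds for the two warfarin branches. A Section 9.1 major bleed that is not life-threatening meets both, and they contradict each other on fresh frozen plasma and differ on PCC and on vitamin K route. This rests on the words of the scope sentence, the two triggers and the major-bleed criteria; no outside figure is needed. The documents do not say how many subjects would fall in the overlap.

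Two secondary mismatches are real but small. The missing PCC row below INR 2.0 is a gap rather than a conflict, softened by the instruction to consult a hematologist. The enoxaparin conversion differs by 10% between two appendices.

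The consequence is inconsistent bleeding-management guidance across sites. Sample size, endpoint definitions and planned analyses are unchanged. The change should be made, but the advisory status of the steps and investigator discretion keep it from being critical.

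**What to change.** Reconcile the two warfarin triggers with each other, with the scope sentence of Appendix 17.8 and with Section 9.1, so that a major bleed within that scope falls under one branch only and the statements on fresh frozen plasma, PCC and vitamin K do not contradict each other. Minor and CRNM bleeds need not be assigned to a branch, because the appendix is scoped to major bleeding. Which regimen applies to which bleed is for the sponsor's clinical experts; this review takes no view.

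In the same edit:

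- Make the any-INR trigger and the INR range of Table 17.6 consistent.
- Use one mg-to-units conversion for enoxaparin in Appendices 17.2 and 17.8.
- Have the fixed and per-kg vitamin K amounts checked against each other across the trial's weight range, as a check rather than a correction.

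The cost is appendix wording at the next amendment and a hematology read-through. No procedure, data item or analysis is added.
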